13.12.11. ICH Listings

- The requirements for each display (i.e. IDSL, ICH etc) specified in the programming notes may be retained, all other reference notes can be deleted.
- Select appropriate standard based on study design (i.e. parallel vs cross-over), when applicable.
- The ADaM datasets for the Core Study Population/Safety displays can be found in the IDSL Library under Reference →Statistical Displays →ADaM Datasets for Core RAP Displays.

ICH: Listings					
No.	Population	IDSL / Example Shell	Title	Programming Notes	Deliverable [Priority]
Subject Disposition					
1.	Screened	ES7	Listing of Reasons for Screen Failure – Part A	Journal Guidelines	SAC
2.	Screened	ES7	Listing of Reasons for Screen Failure – Part B	Journal Guidelines	SAC
3.	Screened	ES7	Listing of Reasons for Screen Failure – Part C	Journal Guidelines	SAC
4.	Safety	CP_ES10x	Listing of Reasons for Study Withdrawal – Part A	ICH E3	SAC
5.	Safety	ES2	Listing of Reasons for Study Withdrawal – Part B	ICH E3	SAC
6.	Safety	CP_ES10x	Listing of Reasons for Study Withdrawal – Part C	ICH E3	SAC
7.	Safety	SD2	Listing of Reasons for Study Treatment Discontinuation – Part B	ICH E3 Required for all studies except single dose studies.	SAC
8.	Safety	BL2	Listing of Participants for Whom the Treatment Blind was Broken – Part A	ICH E3 Blinded studies only.	SAC

ICH: Listings					
No.	Population	IDSL / Example Shell	Title	Programming Notes	Deliverable [Priority]
9.	Safety	BL1	Listing of Participants for Whom the Treatment Blind was Broken – Part B	ICH E3 Blinded studies only.	SAC
10.	Safety	BL2	Listing of Participants for Whom the Treatment Blind was Broken – Part C	ICH E3 Blinded studies only.	SAC
11.	Safety	TA2	Listing of Planned and Actual Treatments – Part A		SAC
12.	Safety	TA1	Listing of Planned and Actual Treatments – Part B		SAC
13.	Safety	TA2	Listing of Planned and Actual Treatments – Part C		SAC
Protocol Deviations					
14.	Safety	DV2A	Listing of Important Protocol Deviations – Part A	ICH E3 Listing also includes analysis population exclusions.	SAC
15.	Safety	DV2	Listing of Important Protocol Deviations – Part B	ICH E3 Listing also includes analysis population exclusions.	SAC
16.	Safety	DV2A	Listing of Important Protocol Deviations – Part C	ICH E3 Listing also includes analysis population exclusions.	SAC
17.	Safety	IE4	Listing of Participants with Inclusion/Exclusion Criteria Deviations – Part A	ICH E3	SAC

ICH: Listings					
No.	Population	IDSL / Example Shell	Title	Programming Notes	Deliverable [Priority]
18.	Safety	IE3	Listing of Participants with Inclusion/Exclusion Criteria Deviations – Part B	ICH E3	SAC
19.	Safety	IE4	Listing of Participants with Inclusion/Exclusion Criteria Deviations – Part C	ICH E3	SAC
Populations Analysed					
20.	Randomized	SP3a	Listing of Participants Excluded from Any Population – Part A	ICH E3 e.g., participants screened but not randomized, participants randomized but not treated, participants with deviations leading to exclusion from per protocol population (can be separate listing per population).	SAC

ICH: Listings					
No.	Population	IDSL / Example Shell	Title	Programming Notes	Deliverable [Priority]
21.	Randomized	SP3	Listing of Participants Excluded from Any Population – Part B	ICH E3 e.g., participants screened but not randomized, participants randomized but not treated, participants with deviations leading to exclusion from per protocol population (can be separate listing per population).	SAC
22.	Randomized	SP3a	Listing of Participants Excluded from Any Population – Part C	ICH E3 e.g., participants screened but not randomized, participants randomized but not treated, participants with deviations leading to exclusion from per protocol population (can be separate listing per population).	SAC
Demographic and Baseline Characteristics					

CONFIDENTIAL

209275

ICH: Listings					
No.	Population	IDSL / Example Shell	Title	Programming Notes	Deliverable [Priority]
23.	Safety	DM4	Listing of Demographic Characteristics – Part A	ICH E3	SAC
24.	Safety	DM2	Listing of Demographic Characteristics – Part B	ICH E3	SAC
25.	Safety	DM4	Listing of Demographic Characteristics – Part C	ICH E3	SAC
26.	Safety	SU2	Listing of Substance Use – Part A		SAC
27.	Safety	SU2	Listing of Substance Use – Part B		SAC
28.	Safety	SU2	Listing of Substance Use – Part C		SAC
Prior and Concomitant Medications					
29.	Safety	CP_CM4	Listing of Concomitant Medications Using Generic Term – Part A		SAC
30.	Safety	CP_CM3	Listing of Concomitant Medications Using Generic Term – Part B		SAC
31.	Safety	CP_CM4	Listing of Concomitant Medications Using Generic Term – Part C		SAC
32.	Safety	MH3	Listing of Medical Conditions – Part A		SAC
33.	Safety	MH2	Listing of Medical Conditions – Part B		SAC
34.	Safety	MH3	Listing of Medical Conditions – Part C		SAC
35.	Safety	FH5	Listing of Family History Conditions – Part A		SAC
36.	Safety	FH5	Listing of Family History Conditions – Part B		SAC
37.	Safety	FH5	Listing of Family History Conditions – Part C		SAC
Exposure and Treatment Compliance					
38.	Safety	EX4	Listing of Exposure Data – Part A	ICH E3	SAC
39.	Safety	EX3	Listing of Exposure Data – Part B	ICH E3	SAC
40.	Safety	EX4	Listing of Exposure Data – Part C	ICH E3	SAC
Adverse Events					

CONFIDENTIAL

209275

ICH: Listings					
No.	Population	IDSL / Example Shell	Title	Programming Notes	Deliverable [Priority]
41.	Safety	CP_AE9	Listing of All Adverse Events – Part A	ICH E3	SAC
42.	Safety	CP_AE8	Listing of All Adverse Events – Part B	ICH E3	SAC
43.	Safety	CP_AE9	Listing of All Adverse Events – Part C	ICH E3	SAC
44.	Safety	CP_AE9	Listing of Drug Related Adverse Events – Part A	ICH E3 Fatal and Non-Fatal SAEs are combined into a single listing for ClinPharm studies (i.e., “Listing of Serious Adverse Events”).	SAC
45.	Safety	CP_AE8	Listing of Drug Related Adverse Events – Part B	ICH E3 Fatal and Non-Fatal SAEs are combined into a single listing for ClinPharm studies (i.e., “Listing of Serious Adverse Events”).	SAC

ICH: Listings					
No.	Population	IDSL / Example Shell	Title	Programming Notes	Deliverable [Priority]
46.	Safety	CP_AE9	Listing of Drug Related Adverse Events – Part C	ICH E3 Fatal and Non-Fatal SAEs are combined into a single listing for ClinPharm studies (i.e., “Listing of Serious Adverse Events”).	SAC
47.	Safety	AE7	Listing of Subject Numbers for Individual Adverse Events – Part A	ICH E3	SAC
48.	Safety	AE7	Listing of Subject Numbers for Individual Adverse Events – Part B	ICH E3	SAC
49.	Safety	AE7	Listing of Subject Numbers for Individual Adverse Events – Part C	ICH E3	SAC
50.	Safety	AE2	Listing of Relationship Between Adverse Event System Organ Classes, Preferred Terms, and Verbatim Text – Part A	IDSL	SAC
51.	Safety	AE2	Listing of Relationship Between Adverse Event System Organ Classes, Preferred Terms, and Verbatim Text – Part B	IDSL	SAC
52.	Safety	AE2	Listing of Relationship Between Adverse Event System Organ Classes, Preferred Terms, and Verbatim Text – Part C	IDSL	SAC
Serious and Other Significant Adverse Events					

ICH: Listings					
No.	Population	IDSL / Example Shell	Title	Programming Notes	Deliverable [Priority]
53.	Safety	CP_AE9a	Listing of Serious Adverse Events (Fatal & Non-Fatal) – Part A	ICH E3 Fatal and Non-Fatal SAEs are combined into a single listing for ClinPharm studies (i.e., “Listing of Serious Adverse Events”).	SAC
54.	Safety	CP_AE8a	Listing of Serious Adverse Events (Fatal & Non-Fatal) – Part B	ICH E3 Fatal and Non-Fatal SAEs are combined into a single listing for ClinPharm studies (i.e., “Listing of Serious Adverse Events”).	SAC
55.	Safety	CP_AE9a	Listing of Serious Adverse Events (Fatal & Non-Fatal) – Part C	ICH E3 Fatal and Non-Fatal SAEs are combined into a single listing for ClinPharm studies (i.e., “Listing of Serious Adverse Events”).	SAC
56.	Safety	CP_AE9	Listing of Adverse Events Leading to Withdrawal from Study – Part A	ICH E3	SAC
57.	Safety	CP_AE8	Listing of Adverse Events Leading to Withdrawal from Study – Part B	ICH E3	SAC

CONFIDENTIAL

209275

ICH: Listings					
No.	Population	IDSL / Example Shell	Title	Programming Notes	Deliverable [Priority]
58.	Safety	CP_AE9	Listing of Adverse Events Leading to Withdrawal from Study – Part C	ICH E3	SAC
Liver events					
59.	Safety	LIVER5	Listing of Liver Monitoring/Stopping Event Reporting – Part A	IDSL	SAC
60.	Safety	LIVER5	Listing of Liver Monitoring/Stopping Event Reporting – Part B	IDSL	SAC
61.	Safety	LIVER5	Listing of Liver Monitoring/Stopping Event Reporting – Part C	IDSL	SAC
62.	Safety	LIVER7	Listing of Liver Biopsy Details – Part A		SAC
63.	Safety	LIVER7	Listing of Liver Biopsy Details – Part B		SAC
64.	Safety	LIVER7	Listing of Liver Biopsy Details – Part C		SAC
65.	Safety	LIVER8	Listing of Liver Imaging Details – Part A		SAC
66.	Safety	LIVER8	Listing of Liver Imaging Details – Part B		SAC
67.	Safety	LIVER8	Listing of Liver Imaging Details – Part C		SAC
All Laboratory					
68.	Safety	LB14	Listing of Clinical Chemistry Laboratory Data with Character Results – Part A	ICH E3	SAC
69.	Safety	LB14	Listing of Clinical Chemistry Laboratory Data with Character Results – Part B	ICH E3	SAC
70.	Safety	LB14	Listing of Clinical Chemistry Laboratory Data with Character Results – Part C	ICH E3	SAC
71.	Safety	CP_LB6	Listing of All Clinical Chemistry Laboratory Data for Subjects with PCI Abnormalities – Part A	Add 'Lab test' column before 'Treatment/Period' column'	SAC
72.	Safety	CP_LB5	Listing of All Clinical Chemistry Laboratory Data for Subjects with PCI Abnormalities – Part B	Add 'Lab test' column before 'Treatment/Period' column'	SAC

CONFIDENTIAL

209275

ICH: Listings					
No.	Population	IDSL / Example Shell	Title	Programming Notes	Deliverable [Priority]
73.	Safety	CP_LB6	Listing of All Clinical Chemistry Laboratory Data for Subjects with PCI Abnormalities – Part C	Add 'Lab test' column before 'Treatment/Period' column'	SAC
74.	Safety	CP_LB6	Listing of Clinical Chemistry Abnormalities of Potential Clinical Importance – Part A	Add 'Lab test' column before 'Treatment/Period' column'	SAC
75.	Safety	CP_LB5	Listing of Clinical Chemistry Abnormalities of Potential Clinical Importance – Part B	Add 'Lab test' column before 'Treatment/Period' column'	SAC
76.	Safety	CP_LB6	Listing of Clinical Chemistry Abnormalities of Potential Clinical Importance – Part C	Add 'Lab test' column before 'Treatment/Period' column'	SAC
77.	Safety	LB14	Listing of Haematology Laboratory Data with Character Results – Part A	ICH E3 'Treatment/Period' will be included as column and will be added after 'Lab Test'	SAC
78.	Safety	LB14	Listing of Haematology Laboratory Data with Character Results – Part B	ICH E3	SAC
79.	Safety	LB14	Listing of Haematology Laboratory Data with Character Results – Part C	ICH E3	SAC
80.	Safety	CP_LB6	Listing of All Haematology Laboratory Data for Subjects with PCI Abnormalities – Part A	Add 'Lab test' column before 'Treatment/Period' column'	SAC
81.	Safety	CP_LB5	Listing of All Haematology Laboratory Data for Subjects with PCI Abnormalities – Part B	Add 'Lab test' column before 'Treatment/Period' column'	SAC

CONFIDENTIAL

209275

ICH: Listings					
No.	Population	IDSL / Example Shell	Title	Programming Notes	Deliverable [Priority]
82.	Safety	CP_LB6	Listing of All Haematology Laboratory Data for Subjects with PCI Abnormalities – Part C	Add 'Lab test' column before 'Treatment/Period' column'	SAC
83.	Safety	CP_LB6	Listing of Haematology Abnormalities of Potential Clinical Importance – Part A	Add 'Lab test' column before 'Treatment/Period' column'	SAC
84.	Safety	CP_LB5	Listing of Haematology Abnormalities of Potential Clinical Importance – Part B	Add 'Lab test' column before 'Treatment/Period' column'	SAC
85.	Safety	CP_LB6	Listing of Haematology Abnormalities of Potential Clinical Importance – Part C	Add 'Lab test' column before 'Treatment/Period' column'	SAC
86.	Safety	LB14	Listing of Hormone Assessment Data with Character Results – Part B	ICH E3	SAC
87.	Safety	LB14	Listing of Urinalysis Data with Character Results – Part A	ICH E3	SAC
88.	Safety	LB14	Listing of Urinalysis Laboratory Data with Character Results – Part B	ICH E3	SAC
89.	Safety	LB14	Listing of Urinalysis Laboratory Data with Character Results – Part C	ICH E3	SAC
90.	Safety	UR2B	Listing of Urinalysis Data for Participants with Any Value of Potential Clinical Importance – Part A	ICH E3 Display ALL data for a subject who experienced a value of potential clinical importance.	SAC

ICH: Listings					
No.	Population	IDSL / Example Shell	Title	Programming Notes	Deliverable [Priority]
91.	Safety	UR2A	Listing of Urinalysis Data for Participants with Any Value of Potential Clinical Importance – Part B	ICH E3 Display ALL data for a subject who experienced a value of potential clinical importance.	SAC
92.	Safety	UR2B	Listing of Urinalysis Data for Participants with Any Value of Potential Clinical Importance – Part C	ICH E3 Display ALL data for a subject who experienced a value of potential clinical importance.	SAC
ECG					
93.	Safety	CP_EG4	Listing of All ECG Values for Subjects with any Value of Potential Clinical Importance – Part A	IDSL Required for ClinPharm studies only. Display ALL ECGs for a subject who experienced a value of potential clinical importance.	SAC

ICH: Listings					
No.	Population	IDSL / Example Shell	Title	Programming Notes	Deliverable [Priority]
94.	Safety	CP_EG3	Listing of All ECG Values for Subjects with any Value of Potential Clinical Importance – Part B	IDSL Required for ClinPharm studies only. Display ALL ECGs for a subject who experienced a value of potential clinical importance.	SAC
95.	Safety	CP_EG4	Listing of All ECG Values for Subjects with any Value of Potential Clinical Importance – Part C	IDSL Required for ClinPharm studies only. Display ALL ECGs for a subject who experienced a value of potential clinical importance.	SAC
96.	Safety	CP_EG4	Listing of ECG Values of Potential Clinical Importance – Part A	IDSL Required for ClinPharm studies only.	SAC
97.	Safety	CP_EG3	Listing of ECG Values of Potential Clinical Importance – Part B	IDSL Required for ClinPharm studies only.	SAC

ICH: Listings					
No.	Population	IDSL / Example Shell	Title	Programming Notes	Deliverable [Priority]
98.	Safety	CP_EG4	Listing of ECG Values of Potential Clinical Importance – Part C	IDSL Required for ClinPharm studies only.	SAC
99.	Safety	CP_EG6	Listing of All ECG Findings for Subjects with an Abnormal Finding – Part A		SAC
100.	Safety	CP_EG5	Listing of All ECG Findings for Subjects with an Abnormal Finding – Part B		SAC
101.	Safety	CP_EG6	Listing of All ECG Findings for Subjects with an Abnormal Finding – Part C		SAC
102.	Safety	CP_EG6	Listing of Abnormal ECG Findings – Part A	IDSL Required for ClinPharm studies only.	SAC
103.	Safety	CP_EG5	Listing of Abnormal ECG Findings – Part B	IDSL Required for ClinPharm studies only.	SAC
104.	Safety	CP_EG6	Listing of Abnormal ECG Findings – Part C	IDSL Required for ClinPharm studies only.	SAC
Vital Signs					

ICH: Listings					
No.	Population	IDSL / Example Shell	Title	Programming Notes	Deliverable [Priority]
105.	Safety	CP_VS5	Listing of All Vital Signs for Subjects with any Value of Potential Clinical Importance – Part A	IDSL Required for ClinPharm studies only. Display ALL Vital Signs for a subject who experienced a value of potential clinical importance.	SAC
106.	Safety	CP_VS4	Listing of All Vital Signs for Subjects with any Value of Potential Clinical Importance – Part B	IDSL Required for ClinPharm studies only. Display ALL Vital Signs for a subject who experienced a value of potential clinical importance.	SAC
107.	Safety	CP_VS5	Listing of All Vital Signs for Subjects with any Value of Potential Clinical Importance – Part C	IDSL Required for ClinPharm studies only. Display ALL Vital Signs for a subject who experienced a value of potential clinical importance.	SAC

ICH: Listings					
No.	Population	IDSL / Example Shell	Title	Programming Notes	Deliverable [Priority]
108.	Safety	CP_VS5	Listing of Vital Signs of Potential Clinical Importance – Part A	IDSL Required for ClinPharm studies only.	SAC
109.	Safety	CP_VS4	Listing of Vital Signs of Potential Clinical Importance – Part B	IDSL Required for ClinPharm studies only.	SAC
110.	Safety	CP_VS5	Listing of Vital Signs of Potential Clinical Importance – Part C	IDSL Required for ClinPharm studies only.	SAC

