5.4. Screen Failures

Screen failures are defined as participants who consent to participate in the clinical study but are not subsequently entered in the study. A minimal set of screen failure information is required to ensure transparent reporting of screen failure participants to meet the Consolidated Standards of Reporting Trials (CONSORT) publishing requirements and to respond to queries from regulatory authorities. Minimal information includes demography, screen failure details, eligibility criteria, and any serious adverse events (SAEs).

Individuals who do not meet the criteria for participation in this study (screen failure) may be rescreened only if the reason for screen failure is an ECG or lab value that, in the opinion of the investigator and/or Medical Monitor, is spurious or needs to be reconfirmed. Rescreened participants should be assigned a new participant number.

Subjects who screen in one Part will not need to be rescreened for another Part, as long as they are within the 30 day screening window. A new subject number and rescreening will only be needed if they are outside the screening window.

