8.3.1. Time Period and Frequency for Collecting AE and SAE Information

- All SAEs will be collected from the start of intervention until the follow-up visit at the time points specified in the SoA (Section 1.3). However, any SAEs assessed as related to study participation (e.g., study intervention, protocol-mandated procedures, invasive tests, or change in existing therapy) or related to a GSK product will be recorded from the time a participant consents to participate in the study.
- All AEs will be collected from the start of intervention until the follow-up visit at the time points specified in the SoA (Section 1.3).
- Medical occurrences that begin before the start of study intervention but after obtaining informed consent will be recorded on the Medical History/Current Medical Conditions section of the CRF not the AE section.
- All SAEs will be recorded and reported to the sponsor or designee immediately and under no circumstance should this exceed 24 hours, as indicated in [Appendix 3](#). The investigator will submit any updated SAE data to the sponsor within 24 hours of it being available.
- Investigators are not obligated to actively seek AEs or SAEs after the conclusion of the study participation. However, if the investigator learns of any SAE, including a death, at any time after a participant has been discharged from the study, and he/she considers the event to be reasonably related to the study intervention or study participation, the investigator must promptly notify the sponsor.

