4. ANALYSIS POPULATIONS

Population	Definition / Criteria	Analyses Evaluated
Screened	All participants who were screened for eligibility	Screen Failures
Randomized	All participants who were randomized	Study Population
Safety	All participants who take at least 1 dose of study intervention. Participants will be analyzed according to the intervention they actually received.	Study Population Safety
PK	Participants in the Safety population for whom a PK sample was taken and analyzed for GSK3439171A and result reported	PK
PD	Participants in the Safety population with at least one PD measure.	PD/Biomarker

Refer to [Appendix 12](#): List of Data Displays which details the population used for each display.
Metabolite ID work will be reported in a separate GSK report

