7. SAFETY ANALYSES

The safety analyses will be based on the safety population, unless otherwise specified.

Descriptive statistics will be used to assess safety and tolerability objectives. No formal statistical analyses of safety data are planned. Data will be summarized according to GSK Integrated Data Standards Library (IDSL) standards for Part A, Part B and Part C separately. In addition, individual participant data will be reviewed. Treatment comparisons with placebo will be based on review of descriptive statistics and individual participant data.

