3.12.	Safety	AE15	Summary of Common (>=10%) Non-serious Adverse Events by System Organ Class and Preferred Term (Number of Participant and Occurrences) – Part B	
FDAAA, EudraCT Disclosure display
 
'Common' to be defined by study/project team. For studies with very few events/participants, listing is sufficient: discuss this option with your disclosure representative.
	SAC

Safety: Tables					
No.	Population	IDSL / Example Shell	Title	Programming Notes	Deliverable [Priority]
3.13.	Safety	AE15	Summary of Common (>=10%) Non-serious Adverse Events by System Organ Class and Preferred Term (Number of Participant and Occurrences) – Part C	FDAAA, EudraCT Disclosure display 'Common' to be defined by study/project team. For studies with very few events/participants, listing is sufficient: discuss this option with your disclosure representative.	SAC
Serious and Other Significant Adverse Events					
3.14.	Safety	AE16	Summary of Serious Adverse Events by System Organ Class and Preferred Term (Number of Participants and Occurrences) - Part A	FDAAA, EudraCT By dose For studies with few events/participants listing is sufficient: discuss this option with your disclosure representative.	SAC
3.15.	Safety	AE16	Summary of Serious Adverse Events by System Organ Class and Preferred Term (Number of Participants and Occurrences) - Part B	FDAAA, EudraCT For studies with few events/participants listing is sufficient: discuss this option with your disclosure representative.	SAC

Safety: Tables					
No.	Population	IDSL / Example Shell	Title	Programming Notes	Deliverable [Priority]
3.16.	Safety	AE16	Summary of Serious Adverse Events by System Organ Class and Preferred Term (Number of Participants and Occurrences) - Part C	FDAAA, EudraCT For studies with few events/participants listing is sufficient: discuss this option with your disclosure representative.	SAC
Laboratory: Chemistry					
3.17.	Safety	LB1	Summary of Clinical Chemistry Values – Part A	By dose Includes Baseline values. Includes pre-specified parameters repeated in conventional units.	SR, SAC
3.18.	Safety	LB1	Summary of Clinical Chemistry Values – Part B	By dose Includes Baseline values. Includes pre-specified parameters repeated in conventional units.	SR, SAC
3.19.	Safety	LB1	Summary of Clinical Chemistry Values – Part C	By treatment group (fed/fasted) Includes Baseline values. Includes pre-specified parameters repeated in conventional units.	SAC

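### No display in the SAP list is specified to show a serious adverse event in a consented participant who is never dosed, although the protocol has some such events recorded

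*SAP*

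**What the plan says.** **Collection.** Protocol 8.3.1 starts general SAE collection at the first administration of study intervention. It makes an exception for "any SAEs assessed as related to study participation", giving required procedures and invasive tests among its examples, and for events related to a product of the sponsor. These are recorded from consent. Protocol 5.4 adds a separate rule for people who consent but do not enter the study: "Minimal information includes demography, screen failure details, eligibility criteria, and any serious adverse events (SAEs". That rule has no limit to related events.

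**Display.** SAP Section 4 defines the Safety population as "All participants who take at least 1 dose of study intervention", and SAP Section 7 states: "The safety analyses will be based on the safety population, unless otherwise specified". In the display lists of SAP Appendix 12, the population column reads Safety for SAE Tables 3.14–3.16, for example "Summary of Serious Adverse Events by System Organ Class and Preferred Term (Number of Participants and Occurrences) - Part A" and "Summary of Serious Adverse Events by System Organ Class and Preferred Term (Number of Participants and Occurrences) - Part B". It also reads Safety for SAE Listings 53–55, for example "Listing of Serious Adverse Events (Fatal & Non-Fatal) – Part A" and "Listing of Serious Adverse Events (Fatal & Non-Fatal) – Part B".

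The SAP also keeps a Screened population, whose stated use in Section 4 is screen failures.

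**The concern.** The protocol asks sites to record certain serious events before the first dose, and the SAP then filters every SAE display on having had a dose. For most participants the two rules do not clash: someone with a pre-dose SAE who is later dosed belongs to the Safety population, and the filter does not remove the event. The clash arises when the event itself stops dosing. The same biopsy complication can be listed if the participant goes on to be dosed, but is left out if it keeps him from being dosed.

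What is at stake is the completeness of the SAE listing. A reader of the report would expect it to account for the serious events that the protocol had recorded, including any caused by an invasive study procedure in a healthy volunteer. As specified, the displays cannot support a statement about SAEs in all consented participants, even a statement that there were none.

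**Working it through.** Apart from the head count in step 4, the check compares the collection rules with the population column of each display.

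1. **Does the protocol generate such records?** Yes, by two routes: 8.3.1 (related events, from consent) and 5.4 (any SAE in a screen failure).

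2. **Does any specified display show them for a never-dosed person?** The candidates are:
   - AE and SAE Tables 3.1–3.16: all Safety.
   - Listings 41–58 (all AEs, drug-related AEs, SAEs, AEs leading to withdrawal and related AE listings): all Safety.
   - Study withdrawal, Listings 4–6: Safety.
   - Medical conditions, Tables 1.27–1.29 and Listings 32–34: Safety. Events that 8.3.1 sends to medical history are therefore not shown there for a never-dosed person either.
   - Screened-population displays: Tables 1.7–1.9 (screening status and failure reasons), Tables 1.13–1.17 (population counts), Listings 1–3 (failure reasons) and Listing 135 (rescreened subjects). None is specified to carry SAEs.
   - Randomized-population displays: Tables 1.21–1.23 (age ranges) and Listings 20–22 (population exclusions). None is specified to carry SAEs.
   - SAP 13.7.1 lists all available data from withdrawn participants unless otherwise specified. The SAE listings do specify otherwise, by naming Safety.

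   No display is left that is specified to show such an event.

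3. **Can the situation arise?** In the 7-day Part B schedule (Protocol 1.3), the first muscle biopsy is on Day -1, and randomization and the first dose are on Day 1. Protocol 4.1 describes a pre-dose biopsy for Part B generally. Protocol 2.3.1 names pain, bleeding, infection and, very rarely, nerve damage as biopsy risks. A serious complication between biopsy and dosing is therefore possible. It would be recorded under 8.3.1 as related to a study procedure, and the person would be outside the Safety population if not dosed.

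4. **How many people are at risk?** Protocol 9.2 gives about 150 screened and 75 randomized. The second figure reproduces from the planned cohorts: 3 × 9 + 3 × 12 + 12 = 27 + 36 + 12 = 75. So about 150 − 75 = 75 people are planned to be screened but not randomized, across all three parts. This is not the group exposed to the biopsy. The Part B schedule requires eligibility assessments before the pre-dose biopsy, so ordinary screen failures should have left by then. Part B accounts for 36 of the 75 planned participants. The relevant group is those biopsied on Day -1 and then not dosed. The documents give neither their number nor a pre-dose SAE rate, so no probability is calculated here.

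**The case against.** The case on the other side is substantial.

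- **The SAP follows the protocol.** Protocol 9.4.1 places all safety analyses on the Safety population, and the primary objective concerns safety after single and repeat doses. A serious event in someone never dosed says nothing about the drug. A reader might infer from a filter that depends on the event's consequence that the SAE results are subject to selection bias. The documents do not support that: rates by dose are rightly confined to dosed participants and do not change. This objection stands, and it limits the point to the completeness of a listing.
- **The definitions are not uniform.** Protocol 10.3.1 ties an adverse event to use of a study intervention, 10.3.2 says that something that is not an AE cannot be an SAE, and 8.3.1 sends pre-dose occurrences to medical history. This narrows the category. It does not empty it, because 8.3.1 expressly has participation-related SAEs recorded from consent.
- **Section 5.4 is a rule on what to hold.** Demography is on the same minimum list, and the SAP shows demography on the Safety population only (Tables 1.18–1.20, Listings 23–25). The SAP therefore does not treat the 5.4 list as a list of required displays. That is fair, although the purpose given in 5.4 is transparent reporting of screen failures and answering regulators' queries, which a short listing would serve.
- **Nothing is hidden from the sponsor.** SAEs go to the sponsor within 24 hours (Protocol 8.3.1 and 10.3.4). The content of the standard shells, such as ES7, is not in the documents. The claim must therefore stay at what the SAP list specifies.

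**Conclusion.** The point holds as a minor gap. SAEs that the protocol has recorded in consented but never-dosed participants have no specified place in the SAP's displays, because of a population rule that the SAP states.

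Two stronger readings should be resisted. A reader might take 75/150 = 50% as the share of people whose SAEs would be lost. That is the planned share not randomized, and most of them should leave before any biopsy. A reader might also infer that the report would declare zero SAEs when one had occurred. The SAP lists displays and does not fix the report's narrative, and the sponsor would know of the event.

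The conclusion rests on two assumptions: that the titles and programming notes in SAP Appendix 12 describe what the displays contain, and that standard shells not shown here do not add SAE content to the screen-failure outputs.

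**What to change.** Either of two changes is enough:

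- Run SAE Listings 53–55 on the Screened population, with a not-dosed flag and the event date, or the day relative to consent or procedure.
- Leave those listings as they are and add one short listing of SAEs in screened-but-not-dosed participants, stating none if there are none.

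Keep Tables 3.14–3.16 on the Safety population so that rates by dose do not change. The SAP Section 7 default already allows specified exceptions. Protocol 9.4.1 does not, so a line in the SAP Section 2.1 table of changes would record the departure.

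The cost is a little extra programming. SAP 13.6.1 derives study day from the first dose date, so a never-dosed participant has none, and the event date or another reference day is needed. Protocol 5.4 lets a person screened for one part move to another within the screening window, so the listing should also state how a never-dosed person is assigned to a part. A single listing across parts would make that easier. No new data collection is needed.
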